2. REVISION HISTORY

SAP Version	SAP Version Date	Which version of Protocol or Protocol Amendment is the SAP based on? Rationales for Changes if applicable
Version 1.0	June 23, 2017,	Supplemental SAP to final SAP Version 4.0 dated on May 29, 2017 and signed on June 1, 2017

3. INTRODUCTION

This is a Supplemental SAP to final SAP Version 4.0 dated on May 29, 2017 and signed on June 1, 2017. Study was unblinded on June 3, 2017. This document describes supplemental analyses beyond the original planned analyses. For detail of study design, please refer to Protocol RHB-102-01, entitled “Randomized, Placebo-Controlled, Phase 3 Trial of RHB-102 (Ondansetron 24 mg Bimodal Release Tablets) for Presumed Acute Gastroenteritis or Gastritis”. For details of main study analyses, please refer to the final SAP Version 4.0.

4. COVARIATES

The final SAP defined randomization stratification factor as covariate:

- Age (<18, ≥ 18 years of age)

In this supplemental SAP, two additional covariates will be defined. Subjects who are ≥ 18 years of age will be grouped by age terciles. Actual cut-point will be derived based on the distribution of age. Covariate variable Age will be coded as below:

Age	<18	1 st 1/3 group of ≥ 18 years of age	2 nd 1/3 group of ≥ 18 years of age	3 rd 1/3 group of ≥ 18 years of age
Coding	1	2	3	4

Another covariate is Baseline Nausea Severity. Baseline nausea severity will be coded as below:

Baseline nausea severity	No Nausea	Mild Nausea	Moderate Nausea	Severe Nausea	Nausea as bad as can be
Coding	1	2	3	4	5

6. PRIMARY ENDPOINT UNTIL DISCHARGE FROM THE ED

Primary endpoint 2 will be defined as the same as primary endpoint in main SAP except the timeframe will be from 30 minutes of first study dose administration to discharge from ED.

Based on both ITT and Subgroup Population 1, primary endpoint 2 will be analyzed as the same as the primary endpoint, as described in the final SAP.

7. PRIMARY ENDPOINT ANALYSIS (SUBGROUP POPULATION 1) BY AGE

Based on Subgroup Population 1, perform Primary Analysis Table 14.2.1.3 by Age (<18 , ≥ 18 years of age).

8. PRIMARY ENDPOINT ANALYSIS BY AGE TERCILE GROUPS

Based on both ITT and Subgroup Population 1, perform Primary Analysis Table 14.2.1.3 by 3 age tercile groups (as defined in covariate section).

9. LOGISTIC REGRESSIONS

Per final SAP, the primary endpoint was analyzed and tested by using Cochran Mantel Haenszel (CMH) test stratified by age. In order to adjust for covariates, logistic regressions will be used in this supplemental SAP.

In this section, all logistical regression analyses will be performed for both ITT population and Subgroup Population 1.

9.1. Primary endpoint analysis by logistic regression

Primary endpoint will be analyzed using logistic regression with treatment as a factor and age (<18 , ≥ 18 years of age) as a covariate. Pvalues and odds ratios of treatment and age from the logistic regression will be presented. This analysis is to mimic the CMH analysis performed in the final SAP.

9.2. Primary endpoint analysis by logistic regression adjusted by age as continuous variable

Primary endpoint will be analyzed using logistic regression with treatment as a factor and age as a continuous covariate. Pvalues and odds ratios of treatment and age from the logistic regression will be presented.

9.3. Primary endpoint analysis by logistic regression adjusted by baseline nausea severity

Primary endpoint will be analyzed using logistic regression with treatment as a factor and baseline nausea severity as a continuous covariates (as defined in covariate section). Pvalues and odds ratios of treatment and baseline nausea severity from the logistic regression will be presented.

9.4. Primary endpoint analysis by logistic regression adjusted by age and baseline nausea severity

Primary endpoint will be analyzed using logistic regression with treatment as a factor and age as a continuous covariate and baseline nausea severity as a continuous covariate (as defined in covariate section). Pvalues and odds ratios of treatment, age and baseline nausea severity from the logistic regression will be presented.

10. SUCCESS AND FAILURE BY INVESTIGATIVE SITE

A table summarizing success/failure/early dropout or invaluable by treatment and by site will be provided. Sites accrued at least 20 patients will have its own entry and the remaining low recruitment sites will be pulled together. This will be based on ITT population and Subgroup Population 1.

11. HIERARCHICAL ANALYSIS OF REASON FOR TREATMENT FAILURE

Based on ITT population and Subgroup Population 1, a hierarchical analysis of reason for treatment failure will be provided. The failure hierarchical order with code for analysis will be:

1. (code=2) Treatment failure by vomiting, regardless of receipt of IV fluid or rescue medication
2. (code=3) Treatment failure by receipt of IV fluid or rescue med in patients who did not vomit
3. (code=4) Early dropout
4. (code=5) Patients who don't have sufficient information to be evaluated for the primary endpoint

Treatment success will be assigned a code = 1. Distribution of treatment success and failure reasons will be tabulated. Wilcoxon rank sum test will be used to test between RHB-102 arm and Placebo arm.

12. ANALYSIS OF VOMITTING

Based on ITT population and Subgroup population 1, subjects who didn't vomit from 30 minutes after first administration of study medication until 24 hours post first dose will be analyzed by CMH stratified by age. Subjects who have missing vomiting status will be treated as “yes.”

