#### 5.2.3 Procedures after discharge from emergency department:

Any patient who has a post-dosing ECG showing QTc>500 msec must have a follow-up ECG within 72 hours of initial dosing showing resolution of the QTc prolongation. This may be performed on an inpatient or outpatient basis at the investigator's discretion. If the QTc does not decrease below 500 msec during initial follow-up, the medical monitor must be contacted to discuss further follow-up.

If a patient vomits from 30 minutes after taking the first dose of study medication until 24 hours after the first dose of study medication or requires rescue antiemetic or parenteral hydration during that period, even without vomiting, he or she will be considered a treatment failure. In that case, the only post-emergency department follow-up will be a call 72-96 hours after discharge from the emergency department to ascertain whether the patient's symptoms have

resolved, whether any adverse events occurred, and whether the patient required further medical follow-up, either in an emergency department or other medical facility.

Prior to discharge, patients who are treatment successes (i.e., no vomiting, no rescue medication and no parenteral hydration while in emergency department) will be given a diary card to record:

- all episodes of vomiting and bowel movements, with description of each bowel movement
- severity of nausea (on a 5-point Likert scale) three times a day: before breakfast or the time at which the patient usually eats breakfast, between 1:00-2:00 pm, and at bedtime
- any symptoms the patient may have related to gastroenteritis, such as chills, fever, abdominal pain
- adverse events
- medications taken, either for gastroenteritis (study medication and others) or other conditions

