7. ENDPOINTS AND COVARIATES

7.1. Efficacy Endpoint(s)

- 1) Primary Efficacy Endpoint: the proportion of patients who fulfill all the following 3 criteria from 30 minutes after first administration of study medication until 24 hours after the first dose of study medication:
 - a. absence of vomiting
 - b. no use of rescue medication, and
 - c. no intravenous hydration

If all of the above three criteria are fulfilled, the patient is considered a treatment success for the primary analysis. If one or more of the above three criteria are not fulfilled, i.e., the patient either experiences vomiting, receives rescue medication or receives intravenous hydration from 30 minutes through 24 hours after the first dose of study medication, the patient is considered a treatment failure.

Based on the 2nd blinded dry run conducted on [REDACTED], there were 28 subjects who did not have all the information needed to determine per the algorithm used if they met the primary endpoint successfully. For 17 patients, all treated under amendment 1 or 2, in which the primary endpoint was treatment success on emergency department discharge, the reason for not having complete information was the lack of an ER day diary. For these patients, based on all follow up data available, no treatment failure events occurred. Therefore, these patients are considered treatment successes. Among the other eleven, data were reviewed and several queries issued. Based on this review, patients were assessed by the medical monitor to be treatment successes (n=4), failures (n=1) or unknown (n=6). The adjudicated primary endpoint outcomes will be used for the primary analyses.

2) Secondary and Tertiary Efficacy Endpoints:

- Treatment success, as defined above, through 4 days following first dose of study medication
- Proportion of patients who experience or require each of the components of treatment failure:
 - Vomiting
 - Rescue antiemetic therapy
 - Intravenous hydration
- Severity of nausea
- Incidence and severity of diarrhea
- Incidence and severity of other symptoms of gastroenteritis
- Time from first dose of study medication to discharge from ED, extended observation unit or hospital, whichever comes last
- Days to resumption of normal activities (work/school/household)
- Proportion of patients requiring hospitalization
- Proportion of patients returning to emergency department for gastrointestinal symptoms within 4 days of initial discharge

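### Supplemental SAP 12 scores missing vomiting status as vomiting without defining missing: rescue- or IV-only ED failures can be relabelled as vomiters and up to 21 adjudicated successes contradicted, with unknown net direction

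*SAP*

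**What the plan says.** Supplemental SAP section 12 takes patients who did not vomit between 30 minutes and 24 hours after the first dose, in the ITT population and Subgroup Population 1. The endpoint "will be analyzed by CMH stratified by age", and the missing-data rule is "Subjects who have missing vomiting status will be treated as" *yes*. The section says nothing more about what counts as missing.

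Three other places bear on it:

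- **Protocol 5.2.3.** Before discharge, ED successes ("no vomiting, no rescue medication and no parenteral hydration while in emergency department) will be given a diary card"). A patient who fails within 24 hours has one post-ED contact, a call 72-96 hours after discharge, covering symptom resolution, adverse events and further medical care.
- **Supplemental SAP section 11.** Failure by IV fluid or rescue in patients who did not vomit is code 3, separate from failure by vomiting (code 2) and from insufficient information (code 5).
- **SAP 7.1.** At the second blinded dry run "there were 28 subjects who did not have all the information needed" to determine the primary endpoint. "For 17 patients, all treated under amendment 1 or 2", "the reason for not having complete information was the lack of an ER day diary", and they are taken as successes: "For these patients, based on all follow up data available, no treatment failure events occurred". The medical monitor assessed the other eleven as 4 successes, 1 failure and 6 unknown. "The adjudicated primary endpoint outcomes will be used for the primary analyses".

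**The concern.** A vomiting-only analysis is useful because it separates vomiting from the more discretionary decisions to give rescue or IV fluid. Protocol 4.2 allows rescue for severe nausea without vomiting, and Protocol 4.4 makes that patient a failure, so rescue- or IV-only failures are expected by design.

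If such a patient fails in the ED, Protocol 5.2.3 removes the diary and the daily contacts. Discharge is allowed from 4 hours, so up to 24 - 4 = 20 hours of the window may have no vomiting record. In that case failure itself creates the missing value, and the rule then scores it as vomiting. Failures are expected more often on placebo, so this path favours RHB-102. It also conflicts with code 3 one section earlier.

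The second issue is coherence. If section 12 is programmed from raw records, patients counted as vomiting-free in the primary composite could be counted as vomiters in one of its components.

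**Working it through.** **Inputs.** Failure 40% placebo and 20% RHB-102; 128 and 192 patients; two-sided alpha 0.01, power 90% (Protocol 7.1). Adjudication counts (SAP 7.1). The documents do not give the rescue/IV-only share of failures, how many of those patients lack status, or the arm split of the adjudicated successes. All three are assumptions below. Counts are expected values, and tables are crude rather than age-stratified.

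**The plan's own figures.** The two-proportion formula (pooled null variance, ratio 1.5, no continuity correction) gives 127 on placebo and 318 in total, against 320 planned. The adjudication counts close: 4 + 1 + 6 = 11 and 17 + 11 = 28. Adjudicated successes are 17 + 4 = 21, and 21/320 = 6.6%.

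**Path 1: rescue/IV-only failures scored as vomiters.** Let s be the share of failures that are rescue/IV-only (equal in both arms) and m the fraction of those lacking status. Assume that none of them vomited after leaving observation. True vomiting is 20%(1-s) v 40%(1-s). Scored vomiting is 20%(1-s+sm) v 40%(1-s+sm). The difference therefore moves from 20(1-s) to 20(1-s+sm) points. Odds ratios are for no vomiting.

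| s | True difference, OR | m = 0.5 | m = 1 |
|---|---|---|---|
| 25% | 15.0 points, 2.43 | 17.5, 2.54 | 20.0, 2.67 |
| 50% | 10.0 points, 2.25 | 15.0, 2.43 | 20.0, 2.67 |
| 75% | 5.0 points, 2.11 | 12.5, 2.33 | 20.0, 2.67 |

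For s = 50%: (0.90/0.10)/(0.80/0.20) = 2.25; with m = 1, (0.80/0.20)/(0.60/0.40) = 2.67. The relative risk of vomiting stays at 0.50 throughout, because s is equal in both arms. If s differs, the distortion can be larger: with true vomiting of 15% in both arms and rescue/IV-only failure of 5% v 25%, a true difference of 0 becomes 20 points.

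**Path 2: the 21 adjudicated successes scored as vomiters.** Start from s = 50%, i.e. 19.2/192 v 25.6/128 (10.0 points, OR 2.25).

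- Split 60:40 (12.6 and 8.4): 31.8/192 = 16.6% v 34.0/128 = 26.6%; difference 10.0 points, OR 1.82.
- Split in proportion to expected successes (153.6:76.8, so 14 and 7): 33.2/192 = 17.3% v 32.6/128 = 25.5%; difference 8.2 points, OR 1.63.
- The difference rises only if k/128 > (21-k)/192, i.e. k > 8.4, so at least 9 on placebo. The binomial chance of that is 48% if each patient is on placebo with probability 0.40, and 24% with probability 1/3.
- The OR rises only with at least 12 on placebo: k = 11 gives (162.8/29.2)/(91.4/36.6) = 2.23; k = 12 gives (163.8/28.2)/(90.4/37.6) = 2.42.

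**Both paths (m = 1, split 14:7).** (38.4 + 14)/192 = 27.3% v (51.2 + 7)/128 = 45.5%; difference 18.2 points, OR 2.22. Against the true 10.0 points and 2.25, the difference is larger and the OR slightly smaller.

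**The case against.** **Missing as event is the plan's own convention.** SAP 8 imputes unknown primary outcomes as failures. That is why *yes* most likely means vomited, although the endpoint is worded as not vomiting and the polarity is unstated. The convention is less neutral here, because Protocol 5.2.3 makes missing status partly a consequence of failing by another component.

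**Code 3 suggests that these patients' status is treated as known.** SAP 8 expects complete ED data, and the programming may count a patient with complete ED observation as non-missing. That may be so, but section 12 does not say it, and ED data alone do not reach 24 hours.

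**Follow-up may have been wider.** The Synopsis methodology, footnote c of the Study Assessments and Protocol 4.5 describe diaries or daily contact for patients generally. Patients who fail after discharge already hold a diary card. The 72-96 hour call asks about symptom resolution, so it may capture some vomiting without dating it to 24 hours. These points stand: the m = 1 column is an upper bound.

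**A reader might infer that SAP 7.1 confines the adjudication to the primary analyses.** It does not. It says the outcomes will be used there and is silent elsewhere. For the 17, it records no failure events in the available follow-up, which implies no known vomiting. That the 21 revert to missing is possible, not stated.

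**A reader might also infer that relabelling the 21 adds to the inflation.** The arithmetic does not support this: at a 60:40 or success-proportional split the difference is unchanged or lower and the OR falls.

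**Observed status is not a bias-free replacement.** Using vomiting up to last observation treats truncated follow-up as vomiting-free. If truncation is commoner on placebo, that errs the other way.

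**Conclusion.** The concern holds as a gap in a stated rule. Section 12 does not define missing or *yes*, does not handle patients who have already failed by rescue or IV fluid, and does not say whether adjudicated outcomes apply. It can classify a code 3 patient as a vomiter.

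The first path can inflate the difference and the OR. The illustration of 10 to 20 points and 2.25 to 2.67 is an upper bound. It assumes a 50% rescue/IV-only share in each arm, no status for any of those patients, and no unrecorded vomiting among them. The relative risk does not move under equal shares, and the effect shrinks if sites collected diaries or daily contacts from failures.

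The second path touches at most 21 patients. It is incoherent with the primary and tends to dilute the effect, although a chance excess on placebo could raise the difference. The net direction cannot be determined from the documents.

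It would go too far to conclude that the primary result is in doubt. Section 12 belongs to a supplement dated June 23, 2017, after unblinding on June 3, and the primary test does not depend on it. The post-unblinding date is a reason to settle these choices in writing.

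**What to change.** In Supplemental SAP section 12:

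1. State that *yes* means vomited, and define when status is missing.
2. Carry the adjudicated 24-hour success status forward as no vomiting.
3. Use one definition of vomiting status in sections 11 and 12, so that rescue/IV-only failures are classified consistently with code 3 and any imputed status is visible as such.
4. Report the age-stratified CMH result with missing scored as vomited and with missing scored as not vomited, as the two bounds. Add observed status as a sensitivity analysis, not as the main result.
5. Tabulate imputed patients by arm and failure reason. This would supply the shares assumed above.

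Separately, reconcile Protocol 5.2.3 with the Synopsis methodology, footnote c of the Study Assessments and Protocol 4.5 on follow-up of failures, and report which was applied in practice.

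The cost is a few lines of SAP text, a few extra runs of one table and one small tabulation. The downside for the sponsor is a possibly less favourable supplemental result.

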13. ANALYSIS OF NAUSEA

Based on ITT population and Subgroup Population 1, time to No Nausea will be displayed using Kaplan-Meier method with pvalues.

Hourly observation data in ED will be used to derive time to the first “No Nausea” as an event or censor. Time to first rescue medication and time to first IV fluid (volume >100 mL) will also be derived for censor. Time to No Nausea will be evaluated based on the following three time duration.

- Time to first No Nausea (for event or censor)
- Time to first rescue (for censor)
- Time to first IV fluid (volume > 100 mL) (for censor)

The earliest event or censor will be used for Time to No Nausea. e.g if the earliest is Time to first No Nausea event, then it will be used as an event. If the earliest is rescue or IV fluid, then the time to first rescue or first IV fluid will be used for censor.

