## **1. Background and Rationale**

### **1.1 Acute Gastroenteritis**

Acute gastroenteritis is inflammation of the stomach, small intestine or large intestine, leading to a combination of abdominal pain, cramping, nausea, vomiting and diarrhea (Graves, 2013). Acute gastritis is inflammation of the stomach; patients with acute gastritis may have vomiting without diarrhea. For purposes of this protocol, patients must present with at least vomiting, as described below, with or without other symptoms.

Acute gastroenteritis is a major health problem worldwide. While mortality is greatest in developing countries and in both the very young and old, morbidity of acute gastroenteritis is shared by all ages and economic strata. In the US, most cases of acute gastroenteritis are viral, most commonly rotavirus and norovirus (Chow et al, 2010; Graves, 2013). In the US, there are between 15-25 million episodes of viral gastroenteritis annually, leading to 3-5 million office visits and 200,000 hospitalizations. While mortality is low, among the 17,000 people dying from acute gastroenteritis in the US each year, 83% are over age 65 (CDC, 2012).

Most cases are self-limited, resolving in one to several days. Mild to moderate cases are generally treated symptomatically. In children, there are guidelines for oral rehydration therapy. More severe and prolonged cases may require diagnostic studies for etiologic organisms. Depending on the severity and etiology, treatment varies from dietary modifications, including oral rehydration therapy, to intravenous fluids and antibiotics. Antiemetics and antidiarrheals are often used. Prochlorperazine and perphenazine are both approved for treatment of nausea and vomiting in general, i.e., including for treatment of acute gastroenteritis. Several other products approved for treatment of nausea and vomiting in special situations, e.g., postoperatively or in association with cancer chemotherapy, are also used for this indication. Ondansetron is often used in both children and adults with acute gastroenteritis, but has never been approved for this indication in any country.

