#### **3.1 Inclusion Criteria**

1. Patients must have vomited at least twice in the 4 hours preceding signing informed consent.
2. A vomiting episode is defined as an episode of forceful expulsion of stomach contents. Retching if a patient has already emptied his or her gastric contents is also considered a vomiting episode. A distinct episode is characterized by a clear break in vomiting activity of at least 5 minutes. Emesis must have been nonbloody (streaks of blood presumed due to force of retching are allowed).
3. All patients (or a parent or guardian for patients  $<$  age 18) must sign informed consent. Patients  $<$  age 18 must also give assent to participate.

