6. ANALYSIS SETS

6.1. Full Analysis Set

The intent-to-treat population (ITT) will consist of all patients who receive any study medication, even if they vomit shortly after administration or are unable to swallow the medication. The primary efficacy analysis will be conducted using ITT population.

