6.2. Subgroup Analysis Sets

6.2.1. Subgroup Population 1

Primary and selected secondary efficacy analyses will also be performed on a predefined subgroup of patients defined as follows:

1. Meet all inclusion/exclusion criteria
2. If they vomit within 15 minutes of receiving the first dose of study medication, receive a second dose
3. Do not have a primary diagnosis on discharge from the ED (or, if admitted, on discharge from the hospital) other than acute gastroenteritis or gastritis

6.2.2. Subgroup Population 2

Another subgroup analysis set will include subjects from sites who enroll 5 or more patients. Analyses of the primary and the first secondary endpoint (treatment success through 4 days) will be performed. Nine of the 21 sites which enrolled patients enrolled fewer than 5 each; this group comprised 7% of total patients treated on study. Patients from these sites had a disproportionately high incidence of major protocol deviations, 42% versus 6% for patients from

sites which enrolled at least 5 patients. Several of these sites appeared to have significant difficulty not only enrolling but also in following protocol procedures. Accordingly, analyzing results excluding these sites is another sensitivity analysis, akin to a per protocol analysis.

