9.2. Analyses of Primary Endpoint

Primary efficacy analysis will be based on the ITT population. The primary endpoint will be tested by Cochran Mantel Haenszel (CMH) test stratified by age. Common odds ratio and its 95% confidence interval will be provided. If the observed 2-sided p-value from the CMH test is

less than 0.05, statistical significance will be declared. Point estimates of the proportions for each treatment arm will be provided along with the corresponding 2-sided 95% confidence intervals. The point estimate of the difference of the proportions between treatment arms will also be provided along with corresponding 2-sided 95% confidence intervals.

For the above primary analysis, Patients who drop out of the study and patients who have unknown primary endpoint will be imputed as failures/non-responders, as stated in the handling of missing value section above.

As a sensitivity analysis, patients who drop out of the study and patients who have unknown primary endpoint will be imputed as responders. The primary analysis of CHM by age will be repeated.

One additional sensitivity analysis, the most conservative approach, will have following imputations:

- patients who drop out of the study and patients who have unknown primary endpoint in active arm will be imputed as failures/non-responders
- patients who drop out of the study and patients who have unknown primary endpoint in placebo arm will be imputed as responders

In addition, subgroup analyses by each age group (<18 , ≥ 18 years of age) will be conducted. For a given age group, unstratified CMH test will be performed. Furthermore, subgroup analyses by baseline nausea severity will also be conducted. None and mild severity will be combined as one group. For a given severity group, unstratified CMH test will be performed.

Primary analysis will also be performed on Subgroup Population 1 and Subgroup Population 2.

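### Supplemental SAP 13 analyses Time to No Nausea without requiring nausea before dosing, which is expected to dilute the comparison by roughly the share of patients who had none

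*SAP*

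**What the plan says.** Supplemental SAP 13 sets the populations and the method: in the ITT set and in Subgroup Population 1, "time to No Nausea will be displayed using Kaplan-Meier method with pvalues". The hourly ED observations supply the event, which is the first record of no nausea. Rescue medication or IV fluid above 100 mL censors the patient if it comes earlier. The section sets no condition on nausea before dosing and has no rule for a patient who starts without it.

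The two populations do not supply that condition. Under SAP 6.1 the ITT set "will consist of all patients who receive any study medication". Under SAP 6.2.1, Subgroup Population 1 asks that patients "Meet all inclusion/exclusion criteria", that early vomiters be redosed, and that there be no other discharge diagnosis.

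Eligibility does not supply it either. Protocol 3.1 says "Patients must have vomited at least twice in the 4 hours preceding signing informed consent", and Protocol 1.1 says "patients must present with at least vomiting, as described below, with or without other symptoms".

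The plan does allow for patients without nausea at baseline. SAP 9.2, on baseline severity subgroups, says "None and mild severity will be combined as one group". Supplemental SAP 4 says "Baseline nausea severity will be coded as below" and gives code 1 to no nausea. Protocol 5.2.2 has nausea scored from 0 to 4 at consent, just before the first dose, hourly, and before ED discharge.

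**The concern.** A curve labelled Time to No Nausea will be read as the time it takes for nausea to go away. A patient without nausea before dosing has nothing to resolve, yet the written rule can score that patient as an event at the first hourly check. Such patients lift both curves at the first time point whatever treatment they received. They carry no information about how fast the drug relieves nausea, so the treatment contrast is expected to move toward no difference. The curves then mix patients whose nausea resolved with patients who had none, and the plan asks for no count that would let a reader separate them.

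**Working it through.** **Plan's own figure.** The documents give no sample size, power or event count for Time to No Nausea, so there is none to reproduce for this analysis. The only design figure is for the 24-hour primary endpoint in Protocol 7.1: 320 patients (192 + 128) for failure rates of 40% and 20%, two-sided 0.01, 90% power. The normal approximation without continuity correction gives 127 + 191 = 318, which agrees. It does not bear on this point, except that the arm sizes are used below.

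**Step 1, the rule applied.** Take a patient with a pre-dose score of 0.
- Still 0 at the first hourly check, with no earlier rescue or IV fluid: event at about 1 hour.
- Nauseated by the first check: stays at risk until a later record of no nausea.
- Rescue or IV fluid above 100 mL first: censored.

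Only the first case is the problem.

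**Step 2, effect on the curves.** Let F(t) be the cumulative event proportion among patients with nausea before dosing, and f the fraction without it, equal in both arms. If all of the latter follow the first case and censoring is ignored, each arm's curve becomes f + (1 - f)F(t). The difference between arms is

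[f + (1 - f)F1] - [f + (1 - f)F0] = (1 - f)(F1 - F0).

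For an assumed gap of 15 points:
- f = 5%: 15 × 0.95 = 14.25
- f = 10%: 15 × 0.90 = 13.5

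**Step 3, effect on the test.** This is a simulated log-rank comparison on an hourly grid from 1 to 4 hours with 192 and 128 patients and 3,000 runs per case. Assumed inputs are hourly resolution of 0.15 on placebo and 0.23 on RHB-102, no rescue or IV censoring, and every patient without baseline nausea scored as an event at hour 1. Power is the rate of rejection in favour of RHB-102 at one-sided 2.5%.

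| f | Hazard ratio, all patients | Hazard ratio, nauseated only | Power, all | Power, nauseated only |
|---|---|---|---|---|
| 0% | 1.53 | 1.54 | 87% | 88% |
| 5% | 1.48 | 1.54 | 84% | 87% |
| 10% | 1.42 | 1.53 | 78% | 83% |
| 20% | 1.34 | 1.53 | 68% | 79% |

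The event share at hour 1 on placebo, all patients included, is 15%, 19%, 24% and 32% for the four values of f. At f = 0 the two analyses are the same in principle, yet the simulated powers differ by 1.5 points (86.9% and 88.4%). That is simulation noise, so the 3-point difference at f = 5% should be read loosely.

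**Step 4, no true effect.** With 0.15 per hour in both arms, the rejection rate in favour of RHB-102 lies between 1.8% and 3.0% over all cases, around the nominal 2.5%. This is expected, because pre-dose nausea precedes treatment.

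**The case against.** The strongest reply is that nobody need be affected. A coding table lists every level of a scale whether or not it is used, and pooling none with mild is what one would do if the none group were nearly empty. Every patient had vomited at least twice within 4 hours of consent. The value of f, the 15-point gap and the hourly rates are not in the documents. All of this stands, and the sizes above are illustrations only.

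The second reply is that time until a patient is recorded free of nausea, in everyone treated, is a legitimate quantity, and Section 13 does not use the word resolution. That is fair. It is a reason to keep the all-ITT version in view, but not to leave it as the only one.

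Third, the supplement is dated June 23, 2017 and the study was unblinded on June 3, 2017. Changing the analysis set now adds a choice made when unblinded data were available. This also stands and is carried into the fix.

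A reader might infer more than the text supports:
- That these patients cannot have the event. Under the written rule they can; what they cannot have is a resolution.
- That they are all immediate successes. Some may be nauseated by the first check, or censored first.
- That the analysis no longer measures relief of nausea. A 15-point gap that reads 14.3 is mild dilution.
- That a median would be reported which nauseated patients never reached. With f = 10% and an arm at 45%, the curve reads 0.10 + 0.90 × 0.45 = 50.5%, but the 45% is chosen to straddle one half. Section 13 itself mentions only a Kaplan-Meier display and p-values; medians come from SAP 9.3.

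Section 5 of the supplement is not in the text available here. Section 13 names its own populations and does not refer to it.

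**Conclusion.** The point holds as a small improvement to one supplemental analysis. As written, a patient with no nausea before dosing who stays that way is counted as an event at the first hourly check. The expected consequence is higher early curves in both arms and a treatment contrast reduced by roughly f. Under the simulation's assumptions, f between 5% and 20% takes the hazard ratio from about 1.53 to between 1.48 and 1.34, and costs about 3 to 11 points of power against the restricted analysis.

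The size rests on f, which is not given and may be zero, and on all such patients scoring at the first check in equal proportion in the two arms. In a single trial, chance imbalance in their number could move the result either way.

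It would be wrong to infer a false-positive problem or any threat to the main conclusion. Type I error is not inflated, the analysis was specified after unblinding and supports no decision rule, and the primary endpoint does not use these data.

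**What to change.** Add one line to Supplemental SAP 13: the Time to No Nausea analysis, in both populations, includes only patients whose last nausea score before the first dose is at least mild. State the threshold on one scale. Mild is score 1 in Protocol 5.2.2 but code 2 in Supplemental SAP 4, where code 1 means no nausea. In the same line, name the time origin. Report the number excluded by arm, and show the all-ITT version alongside.

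The score is already scheduled before treatment and already coded as a covariate, so nothing new has to be collected and conditioning on it keeps the arms comparable. If few patients are excluded, the two versions will nearly coincide and the reader can see that.

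The cost is that a few patients leave this one supplemental analysis. The restriction is itself a change made after unblinding, and the report must say so.
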